3.1.7 Subgroups

No subgroups analyses will be performed.

3.2 Outcome variables

3.2.1 General variables

3.2.1.1 Demographics and baseline characteristic data

Demographics and baseline characteristics will be assessed at screening and/or on date of first administration of study intervention in induction phase (necessarily before first administration). For rescreened subjects, data re-entered at the re-screening visit will be used for analysis.

Demographic variables are age in years, sex, ethnicity, race and country. Following age groups will be created: age group 1: $\geq 18 - <50$, $\geq 50 - <65$, $\geq 65 - <75$, ≥ 75 and age group 2: $\geq 18 - <65$, ≥ 65 in years. Further subject characteristics include height in cm, weight in kg and body mass index (BMI) in kg/m^2 at baseline. Weight groups of <70 , $\geq 70 - <=90$, >90 in kg will be derived. The BMI is calculated as weight in kg divided by (height in m)². BMI groups of $<=25$, $>25 - <=30$, >30 kg/m^2 will be derived.

The BMI will be calculated considering the following formula $\text{BMI} (\text{kg}/\text{m}^2) = \text{weight} / (\text{height})^2$. To evaluate nicotine, use and consumption, number of pack years as number of pack-years = (number of packs / day) * numbers of years smoking will be calculated. Number of years smoking is calculated as (end date – start date +1)/365.25 (in case of missing or partial dates, imputed dates will be used for this calculation, see section 3.1.5). The end date for current substance usage will be the date of the screening (or re-screening) visit. If subject provides information on number of packs per week instead of per day, number of packs will be divided by 7 to be used in this formula.

Time (weeks) from original diagnosis to first administration in induction phase will be derived as

$$(\text{date of first administration in induction phase} - \text{date of original diagnosis} + 1)/7.$$

In case of missing date of original diagnosis, use imputed date instead, see section 3.1.5.

Subject recruitment will be also presented by region, country and center using the following regional groups: Asia (S. Korea), Europe (Spain, Poland) and North America (United States, Canada).

3.2.1.2 Medical history

The Medical Dictionary for Regulatory Activities (MedDRA) (using the latest or current MedDRA version) will be used to code the medical history.

3.2.1.3 Prior/Concomitant medications and post-discontinuation therapy

The latest or current World Health Organization Drug Dictionary (WHODD) at the time of reporting will be used to code any medications.

Any medications taken by the subject at any time between the date of the first administration of study intervention in induction phase (including the date of the first administration) up to the date of last administration of study intervention (regardless of phase) + 90 days in the study will be considered as concomitant medication. Any medication that started prior to the first administration of the study intervention in induction phase and ended after the first administration or is ongoing will be considered as both prior and concomitant medication. In a similar way, medications can be concomitant for both phases, induction and maintenance phase, and will be summarized in both phases accordingly. A flag will be used to identify in the listing breakthrough pain medication and antibiotics.

As per protocol sections 6.5.1 and 6.5.2, concomitant medications will be categorized into permitted (allowed) and prohibited (disallowed) medications. Allowed medication will be summarized including details for G-CSF as prophylaxis or treatment for adverse events. Prohibited medications will be listed only.

Subsequent therapies (chemotherapy or immunotherapy) received after discontinuation of IP will be listed. Radiotherapy received after discontinuation of IP will be listed separately. Therapy received on the same day as discontinuation of study treatment will be considered to be a subsequent therapy.

3.2.1.4 Duration of exposure

Duration of exposure is defined as:

- Total treatment duration (days) = (min(last dose date where dose > 0 [units] + xx days, date of death, date of DCO) – date of first dose +1), where xx days equal the following dependent on treatment:

Durvalumab	xx days = CCI
Etoposide (last dose date on Day 1 of a cycle)	xx days =
Etoposide (last dose date on Day 2 of a cycle)	xx days =
Etoposide (last dose date on Day 3 of a cycle)	xx days =
Carboplatin	xx days =
Cisplatin	xx days =
AZD2811	xx days =

- Actual treatment duration = total treatment duration, excluding total duration of dose interruptions and cycle delays. The duration of dose delays/interruptions will be the sum of positive values of [Date of the dose -Date of previous dose - (C +xx) days] where xx is 3 days for induction and 1 day for maintenance (window around visit as for protocol schedule of activities).

To convert treatment duration from days to weeks, the duration will be divided by 7 and from days to years, the duration will be divided by 365.25.

For durvalumab, the total treatment duration and actual treatment duration will be calculated separately for induction and maintenance phase as well; using first/last dose date in the respective phase only in the derivation.

For subjects who continued into maintenance without delay on CCI the cut-off for Durvalumab exposure will be the day before the first dose in maintenance.

Exposure will also be measured by the number of cycles received. A cycle corresponds to a period of C. If a cycle is prolonged due to toxicity, this should still be counted as one cycle. A cycle will be counted if treatment is started even if the full dose is not delivered.

A dose modification is either a, dose interruption and/or dose reduction as collected in the eCRF.

For handling exposure and dose interruptions, the following rules will be considered.

Subjects who permanently discontinue during a dose interruption

If a subject permanently discontinues study treatment during a dose interruption, then the date of last administration of study intervention recorded on the appropriate exposure eCRF form will be used in the programming. See further Appendix B.

3.2.1.5 Dose intensity

Dose intensity of investigational products (IP) (AZD2811 and durvalumab only) will be addressed by considering relative dose intensities (RDI).

Relative dose intensity is the percentage of the actual dose delivered relative to the intended dose through to treatment discontinuation. Relative dose intensity will be defined as follows:

- RDI = $100\% * d/D$, where d is the actual cumulative dose delivered up to the actual last day of dosing and D is the intended cumulative dose up to the actual last day of dosing. D is the total dose that would be delivered, if there were no modification to dose or schedule (i.e. dose interruptions and/or cycle delays).

When deriving actual dose administered the volume before and after infusion will also be considered.

Subsequent to the review of the safety run-in cohort of the current study (see CSP Section 4.1.2.2.1), the starting dose of AZD2811, in combination with durvalumab in the maintenance phase, has been reduced to a maximum of CCI on CCI. This will be considered when defining the intended dose for patients treated with AZD2811 after the 28th September 2021.

3.2.2 Primary outcome variables

The primary outcome variable which addresses the efficacy of AZD2811 is described in Section 9.4.2.1 of the CSP.

3.2.2.1 Progression free survival (PFS)

PFS is defined as the time from first administration of study intervention in the induction phase until the date of the first documented (subsequently confirmed) disease progression or death (by any cause in the absence of progression) regardless of whether the subject withdraws from study therapy or receives another anti-cancer therapy prior to progression (i.e. date of PFS event (progression/death) or censoring – date of first administration of study intervention + 1). Subjects who have not progressed or died at the time of analysis will be censored at the time of the latest date of assessment from their last evaluable RECIST assessment.

However, if the subject progresses or dies immediately after two or more consecutive missed visits, the subject will be censored at the time of the latest evaluable RECIST assessment prior to the two missed visits. Note: A NE visit is not considered as a missed visit.

Given the scheduled visit assessment scheme (i.e. CCI for the first 36 weeks then CCI thereafter) the definition of 2 missed visits will change. If the previous RECIST assessment is less than study day 204 (i.e. week 29: week 30 – 1 week for early assessment) then two missing visits will equate to CCI since the previous RECIST assessment, allowing for early and late visits (i.e. CCI). If the two missed visits occur over the period when the scheduled frequency of RECIST assessments changes from CCI to CCI this will equate to CCI (i.e., CCI CCI CCI). The time period for the previous RECIST assessment will be from study days 204 to 245 (i.e. week 30 up to week 36). From week 36 onwards (when the scheduling changes to CCI)

CC1 [] assessments), two missing visits will equate to CC1 [] (i.e. CC1 [] + 1 week for an early assessment + 1 week for a late assessment = CC1 []

If the subject has no evaluable visits or does not have baseline data, they will be censored at Day 1 unless they die within 2 visits of baseline (12 weeks plus 1 week allowing for a late assessment within the visit window) in which case, their date of death will be used.

The PFS time will always be derived based on scan/assessment dates not visit dates.

RECIST assessments/scans contributing towards a particular visit may be performed on different dates. The following rules will be applied:

- For investigational assessments, the date of progression will be determined based on the **earliest** of the dates of the component that triggered the progression
- When censoring a subject for PFS the subject will be censored at the **latest** of the dates contributing to a particular overall visit assessment

Note: for TLs only the latest scan date is recorded out of all scans performed at that assessment for the TLs and similarly for NTLs only the latest scan date is recorded out of all scans performed at that assessment for the NTLs.

Days prior to progression for discontinued subjects will be calculated as date of progression – date of treatment discontinuation + 1.

For days between RECIST assessments, days will be calculated as date from next assessment – date from latest scan date + 1 and averaged for a subject. The first post baseline RECIST assessment is compared to the date of first administration of study intervention in induction phase.

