9.4.2 Efficacy

From CSP v8.0 onwards, the starting dose of AZD2811 in the maintenance phase was CCI [REDACTED], the study will therefore primarily report efficacy for the CCI [REDACTED] AZD2811 dose. Further sensitivity analyses will be defined in the SAP.

From CSP v9.0 onwards, study enrolment has been terminated and the study will proceed to final analysis and an abbreviated CSR. As a result of this, efficacy analyses will be streamlined as there were too few patients who received AZD2811 in combination with durvalumab (9 patients) to give meaningful analyses.

Sections below containing original plans for reporting efficacy are retained for reference but notable changes will include:

- No summaries of efficacy data will be provided, with the exception of PK, and selected efficacy data will be listed only.
- DoR, PFS2, PRO and breakthrough pain therapy endpoints will no longer be reported in the abbreviated CSR.

Full details of planned efficacy analyses will be documented in the SAP.

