9.4.2.1 Primary Endpoint(s)

The primary efficacy endpoint is landmark PFS APF12, where PFS is defined as the time from the first dose of study intervention in the induction phase until objective disease progression (as assessed by the investigator per RECIST v1.1) or death from any cause, whichever comes first. The primary endpoint will only be summarized for participants who entered the maintenance phase and received [REDACTED] AZD2811 + durvalumab on [REDACTED] Day 1 and includes all data from the first dose of study intervention in the induction phase.

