9.4.2.2 Secondary Endpoints

The secondary efficacy endpoints include landmark OS12, OS15, OS18, landmark PFS APF6 and APF9, and OS, PFS, ORR, PK, and health-related QoL. Unless specified otherwise, the secondary endpoints will only be summarized for participants who receive [REDACTED] AZD2811 + durvalumab in the maintenance phase and include all data from first dose of study intervention in the induction phase. The ORR will be presented for all participants in the induction phase. The ORR will also be presented for all participants who received AZD2811 + durvalumab in the maintenance phase and include all data from first dose of study intervention in the induction phase.

9.4.2.3 [REDACTED]

[REDACTED]

Progression-free survival

The PFS analysis is for those participants who entered the maintenance phase and received AZD2811 + durvalumab on [REDACTED] Day 1.

Progression-free survival is defined as the time interval from the first dose of study intervention in the induction phase until the date of objective disease progression or death (by any cause, in the absence of progression) regardless of whether the participant withdraws from treatment or received another anticancer therapy prior to progression. Participants who have not progressed (defined as CR, PR, or SD by RECIST v1.1) at the time of analysis will be censored at the time of the last evaluable RECIST v1.1 assessment.

However, if the participant progresses or dies after 2 or more consecutively missed radiologic visits, the participant will be censored at the time of the last evaluable RECIST v1.1 assessment prior to the 2 missed visits. Note: A NE visit is not considered as a missed visit. If

the participant is NE post-baseline RECIST v.1.1, they will be censored at Day 1 unless they die within 2 visits of baseline (in which case, their date of death will be used).

Progression-free survival will be derived based on scan/assessment dates, not the scheduled visit dates. If RECIST v1.1 assessments contributing toward a particular visit are performed on different dates, then the date of progression will be determined based on the earliest of the dates of the component that triggered the progression. With regard to censoring, a participant will be censored at the latest of the dates contributing to a particular overall visit assessment.

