1 STUDY OBJECTIVES

This study was designed as a Phase II, open-label, multicenter, single arm, global study to determine the efficacy, safety and tolerability of AZD2811 + durvalumab maintenance therapy in subjects with extensive stage small cell lung cancer (ES-SCLC) who do not progress during etoposide and platinum-based chemotherapy (EP) combined with durvalumab induction therapy as onset of first-line treatment.

According to the original Clinical Study Protocol (CSP), the global recruitment will be completed when approximately 100 eligible subjects are enrolled at sites worldwide. Treatment will be conducted in 2 phases – an initial induction phase followed by a maintenance phase.

However, from CSP v9.0 onwards, the enrolment has been terminated prematurely due to the evolving benefit risk profile of AZD2811 that does not support further development for the first-line treatment of patients with extensive stage small-cell lung cancer.

Information on originally planned study objectives and endpoints, as outlined in Section 3 of the [CSP](#) are presented in Table 1 for reference. However, it should be noted that due to the decision to terminate enrolment prematurely, statistical analyses will be streamlined with respect to efficacy data and the focus of the abbreviated CSR will be on reporting safety data in full as described in this SAP.

In addition, the [CC1](#)

■ will be handled outside the abbreviated clinical study report (CSR) and thus are not part of this statistical analysis plan (SAP).

Table 1 Study Objectives and endpoints

Objectives	Endpoints
Primary	
To evaluate the efficacy of AZD2811 + durvalumab by assessment of the proportion of subjects alive and progression free at 12 months APF12 who have not progressed during EP-durvalumab based induction therapy.	The proportion of subjects alive and progression free at 12 months APF12 will be defined as the Kaplan-Meier estimate of PFS per RECIST v1.1 as assessed by the investigator at local site at 12 months, in subjects who enter the maintenance phase.
Secondary	

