To evaluate efficacy of AZD2811 + durvalumab by assessment of the proportion of subjects alive at 12 months OS12, 15 months OS15, and 18 months OS18 who have not progressed during EP-durvalumab based induction therapy.	The proportion of subjects alive at 12 months OS12, 15 months OS15, and 18 months OS18 will be defined as the Kaplan-Meier estimate of OS at 12 months, 15 months, and 18 months, respectively, in subjects who enter the maintenance phase.

Objectives	Endpoints
To evaluate efficacy of AZD2811 + durvalumab by assessment of the proportion of subjects alive and progression free at 6 months APF6 and 9 months APF9 who have not progressed during EP-durvalumab based induction therapy.	The proportion of subjects alive and progression free at 6 months APF6 and 9 months APF9 will be defined as the Kaplan-Meier estimate of PFS per RECIST v1.1 as assessed by the investigator at local site at 6 months and 9 months, respectively, in subjects who enter the maintenance phase.
To evaluate efficacy of EP-durvalumab by assessment of Objective response rate (ORR) in the induction phase.	ORR is defined as the proportion of subjects with measurable disease at baseline who have a confirmed CR or PR, by the investigator at local site per RECIST v1.1 in the induction phase (all subjects).
To evaluate efficacy of AZD2811 + durvalumab by assessment of ORR in the subjects who had not progressed during EP-durvalumab based induction therapy.	ORR is defined as the proportion of subjects with measurable disease at baseline who have a confirmed CR or PR, by the investigator at local site per RECIST v1.1, in subjects who enter the maintenance phase.
To evaluate efficacy of AZD2811 + durvalumab by assessment of PFS in subjects who had not progressed during EP-durvalumab based induction therapy.	PFS is defined as time from date of first dose study intervention in the induction phase until progression per RECIST v1.1 or death due to any cause. The median Kaplan-Meier estimate in subjects who enter the maintenance phase.
To evaluate efficacy of AZD2811 + durvalumab by assessment of OS in subjects who had not progressed during EP-durvalumab based induction therapy.	OS is defined as time from date of first dose study intervention in the induction phase until the date of death due to any cause. The median Kaplan-Meier estimate in subjects who enter the maintenance phase.

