6 CHANGES OF ANALYSES FROM PROTOCOL

1. Laboratory: The frequency of changes with respect to normal ranges between baseline and each post-treatment time point won't be tabulated. Instead the frequency will be presented for changes between baseline and maximum on treatment only.
2. The number and percentages of subjects with at least one dose interruption and at least one dose reduction will not be presented separately for the planned length of cycles but overall only.
3. Clarification: Given the decision on 14 December 2021 to terminate enrolment, the abbreviated CSR will focus on reporting of safety endpoints as there were a limited number of patients with evaluable data to give meaningful efficacy and CCI [REDACTED]. This was noted in the CSP v9.0 but has been further clarified with additional details of planned analyses in this SAP.

Early Phase Oncology Statistical Analysis Plan

Study Code D6132C00001

Edition Number 2.0

Date 05MAY22

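### SAP Section 3.2.2.1 adds an undeclared confirmation condition to the PFS progression event and gives no rule for a progression that is never confirmed

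*SAP*

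**What the plan says.** **PFS event in the SAP.** Section 3.2.2.1 runs PFS to "the first documented (subsequently confirmed) disease progression or death (by any cause in the absence of progression"). The sentence just before it, in Section 3.2.2, says the primary outcome variable "is described in Section 9.4.2.1 of the CSP".

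**PFS event elsewhere.** Protocol Section 9.4.2.1 measures PFS "until objective disease progression (as assessed by the investigator per RECIST v1.1) or death from any cause, whichever comes first". The PFS text under protocol Section 9.4.2.3 runs it "until the date of objective disease progression or death". SAP Table 1 has "until progression per RECIST v1.1 or death due to any cause". None of these mentions confirmation.

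**Status of those texts.** Protocol Section 9.4.2 says: "Sections below containing original plans for reporting efficacy are retained for reference but notable changes will include". The changes it then lists do not mention confirmation, and it leaves full details to the SAP. SAP Section 1 says that the planned objectives and endpoints "are presented in Table 1 for reference".

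**Declared changes.** SAP Section 6 has three entries: laboratory shift tables, dose interruptions and reductions, and the scope of the abbreviated report. The third says that the reduced scope "has been further clarified with additional details of planned analyses in this SAP". The SAP amendment history does not mention the PFS event either.

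**Confirmation scans.** Protocol Section 8.1 asks for a further scan after each initial progression in all participants, at least 4 weeks later and by the next scheduled imaging visit. Appendix F 4.1 and F 5 say the same. F 5 gives two purposes: treatment decisions, and separating pseudoprogression from true progression. It tells the investigator to leave the first PD assessment as it is when the next scan does not confirm it.

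**The concern.** A confirmation condition changes which assessment is the PFS event. Under the protocol the first RECIST v1.1 PD is the event whatever follows. Under the SAP wording it seems to be the event only if a later scan supports it. The two definitions agree when the next scan confirms the PD. They can differ when it does not, or when the subject dies, withdraws or reaches data cut-off before it.

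The SAP also leaves the rule incomplete. It censors subjects who have neither progressed nor died, but does not say whether a never-confirmed PD counts as having progressed, and it gives no algorithm for confirmation. Two programmers could therefore list different dates, or a different event/censor status, for the same subject. A reader of the listings who relies on the protocol definition would not know that another rule had been used.

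**Working it through.** The plan has no figure to reproduce here, so the check compares the two rules on constructed subjects. The numbers illustrate the mechanism and are not expected effects.

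**Inputs**
- Study day = date − first dose date + 1 (SAP Section 3.1.2), so a scan exactly at week w falls on day 7w + 1. This matches SAP Section 3.2.2.1, where week 29 is day 204: 29 × 7 + 1 = 204.
- Scans at weeks 18, 24, 30 and 36 (protocol Table 3), and every 6 weeks before that (protocol Section 4.1).
- Earliest confirmatory scan: 4 weeks after PD (protocol Section 8.1).
- Data cut-off: 18 June 2022 (SAP Section 3.1.1).
- Assumption: an unconfirmed PD is not counted under the SAP. If it is counted, every difference below is zero.

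**Study days.** Week 18: 18 × 7 + 1 = 127. Week 20: 141. Week 22: 155. Week 30: 211.

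| Constructed subject | Protocol | SAP, natural reading | Difference |
|---|---|---|---|
| PD at week 18, confirmed at week 24 | event, day 127 | event, day 127 | 0 |
| PD at week 18, PR at week 24, PD at week 30 confirmed at week 36 | event, day 127 | event, day 211 | 211 − 127 = 84 days |
| PD at week 18, death at week 20 | event, day 127 | event (death), day 141 | 141 − 127 = 14 days |

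In the third row the earliest permitted confirmatory scan, on day 155, falls after the death, so confirmation was impossible.

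**PD shortly before cut-off.** 18 June 2022 minus 28 days is 21 May 2022. A first PD on any of the 28 days from 22 May to 18 June 2022 cannot be confirmed by cut-off. Take a subject who is alive at cut-off and whose PD scan is the last evaluable assessment. The protocol gives an event and the SAP a censored record. The listed time is the same if all scans for that visit share one date. If they do not, it can differ as well, because SAP Section 3.2.2.1 dates progression by the earliest date of the triggering component and censoring by the latest date of the visit.

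**Best objective response.** SAP Section 3.2.3.2 stops at subsequently confirmed progression in one place and at the first progression event in another. These agree only if the second phrase also means confirmed progression, which is not stated. For the second subject in the table, with SD at weeks 6 and 12, the listed response is PR if the cut is at confirmed PD and SD if it is at the first PD. This holds only if the week-18 PD was not due to a new lesion. While a new lesion is recorded, week 24 is still PD under SAP Section 3.1.6.2, and the response is SD either way.

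**The case against.** **The SAP does not actually say that unconfirmed PD is ignored.** Section 3.1.6 uses RECIST v1.1 data to decide if and when a subject has progressed, Table 6 assigns PD at a single visit, and the dating rules in Section 3.2.2.1 have no confirmation step. This stands in part. A reader might infer that the SAP demonstrably counts only confirmed progression. That is the natural reading of the qualifier, but the documents do not settle it. What they do establish is a qualifier that conflicts with the other definitions and has no rule attached.

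**The protocol hands the details to the SAP.** The old efficacy text and Table 1 are kept for reference, and the protocol's list of changes is not exhaustive. So the sponsor may redefine the event. But SAP Section 3.2.2 still points to protocol Section 9.4.2.1, PFS is still derived and listed, and Section 6 is where such a change should be declared. Its general remark about clarification does not do that.

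**Confirmed progression is a reasonable choice with immunotherapy,** and the protocol has criteria for it. This also stands: declaring and defining it would remove the inconsistency as well as deleting it would. It does not justify leaving it undeclared.

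**Missing confirmation by design.** A reader might infer from Appendix F 5 that subjects who deteriorate are not meant to have a follow-up scan. The documents do not support that. Clinical deterioration appears in only one of the two stated purposes, while the request for a scan in Section 8.1 and Appendix F covers everyone.

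**Materiality.** The analysis is descriptive and efficacy is only listed. The tumor assessment listings will still show the first PD, so either version of PFS can be reconstructed. This stands and limits the severity.

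**Conclusion.** The point holds and is minor. The SAP's PFS event conflicts with the protocol definition it refers to and with its own Table 1. The difference is undeclared, and there is no rule for a first PD that is never confirmed.

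On the natural reading, listed PFS is unchanged for subjects whose first PD is confirmed. For the others it can be later, or an event can become a censored record. The 84-day and 14-day differences rest on constructed sequences, scans exactly on schedule and unconfirmed PD not being counted.

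The number of subjects affected cannot be derived and may be zero. Nine patients received AZD2811 with durvalumab, but the listings cover all subjects assigned to study intervention.

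A reader might infer that the primary endpoint is biased. It is not affected: no Kaplan-Meier estimate, landmark rate or response rate will be produced, so no summary or conclusion changes. The best-response point is a related ambiguity in wording and adds no weight to the PFS point.

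**What to change.** Delete the confirmation qualifier from SAP Sections 3.2.2.1 and 3.2.3.2, so that PFS and best objective response both use the first RECIST v1.1 PD, as in the protocol. If confirmation status is of interest, show it as a flag in the progression listing: confirmed, not confirmed, or not confirmable by data cut-off.

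If the sponsor does intend confirmed progression, declare it in Section 6, define confirmation, state how an unconfirmed or unconfirmable first PD is handled for event status and date, and align Table 1 and Section 3.2.3.2.

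The first option costs two wording deletions and a small derivation change, and the second a few sentences. Neither needs new data. The SAP edition is dated 5 May 2022, ahead of the 18 June 2022 cut-off, so either change could have been made before the final data were available.
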